# 1. CARPENTIER-EDWARDS® PERIMOUNT® MAGNA EASE™ PERICARDIAL BIOPROSTHESES STUDY SUMMARY

Protocol No:	2007-08
Study Title	Carpentier-Edwards Perimount Magna Ease Pericardial Bioprosthesis in the Aortic Position, Model 3300TFX
Study Purpose:	To evaluate the long term safety and effectiveness of the Carpentier-Edwards® PERIMOUNT® Magna Ease™ Valves in patients undergoing isolated aortic valve replacement.
Study Device:	Carpentier-Edwards® PERIMOUNT® Magna Ease™, Model 3300TFX.
Study Design:	This is a prospective, single-arm, multi-center study to be conducted in the US, and outside the US (OUS). This study will enroll a minimum of 225 patients implanted with the study valve in order to achieve 101 aortic valve replacement subjects each followed for a minimum of 8 years.
Study Population:	Male and female patients, 18 years or older, requiring replacement for a diseased, damaged, or malfunctioning natural or prosthetic aortic valve.
Entry Criteria:	Patients will preoperatively sign the patient informed consent form, and meet all inclusion criteria and none of the exclusion criteria to participate in this clinical study.
Duration of Participation:	After valve implantation, patients will be followed and assessed at discharge, 6-months, one year, and annually thereafter for a minimum of 8 years.
Clinical Endpoints:	
Primary Safety
 
Linearized yearly rates of:
 
 
• Thromboembolism
 
• All hemorrhage
 
• All perivalvular leak
 
• Endocarditis
 
 
Secondary Safety
 
Early rates, late linearized rates, and actuarial rates of:
 
 
• Thromboembolism
 
• Valve thrombosis
 
• All hemorrhage
 
• Major hemorrhage
 

PROPRIETARY DATA: This document and the information contained herein may not be reproduced, used or disclosed without written permission from Edwards Lifesciences LLC.

	
 
• All perivalvular leak
 
• Major perivalvular leak
 
• Endocarditis
 
• Hemolysis
 
• Structural valve deterioration
 
• Non-structural valve dysfunction
 
• Reoperation
 
• Explant
 
• Death
 
• Valve-related death
 
 
Blood Data
 
Primary Effectiveness:
 
Percent of subjects in NYHA Functional Class I and II at 8 years post implant.
 
Secondary Effectiveness:
 
Hemodynamic Performance at 8 years post implant:
 
 
• Peak gradient
 
• Mean gradient
 
• Effective orifice area (EOA)
 
• EOA index
 
• Performance index
 
• Cardiac output
 
• Cardiac index
 
• Severity of aortic regurgitation
 
 
Quality of Life survey (EQ-5D)

Study Sponsor:
	
Edwards Lifesciences LLC                  [name]                  [name]

## 2. Carpentier-Edwards Perimount Magna Ease Pericardial Bioprosthesis in the Aortic Position Study Procedures Chart

Required information or Procedure	Assessments					
	Pre-op	Operative	Discharge	6-Month	1 Year, annually thereafter	Unscheduled visit
Subject Informed Consent	X					
Inclusion/Exclusion Criteria	X					
Subject Demographics	X					
History	X					
Diagnosis for Implant		X				
Operative Information		X				
Implant Data Card			X			
Physical Assessment 	X		X	X	X	X
Cardiac Rhythm by EKG	X			X	X	X
Antithromboembolic Therapies	X		X	X	X	X
Coagulation Profile	X		X	X	X	X
NYHA Functional Class	X			X	X	X
Echocardiography	X 	X 	X	X	X 	X 
Blood Data	X			X	X	X
Adverse Events		X	X	X	X	X
Visit / Subject Status			X	X	X	X
QOL XXXXXXXXXX	X			X		

 Physical Assessment includes measurement of heart rate, height (initial assessment only), weight and blood pressure

 If Intra-operative TEE is conducted, echocardiography data should be collected

 Full Echocardiography data is required at 1, 5 and 8 Year follow-up visits.  
 At 2, 4 and 6 Year follow-up visits, an echocardiography with regurgitation data, if present; ejection fractions, gradients EOA, LV Mass and perivalvular leaks.

 Optional

### **3. INTRODUCTION**

Valvular heart disease is a life-threatening disease that afflicts millions of people worldwide and leads to approximately 250,000 valve repairs and/or replacements each year [1]. Diseased heart valves can be treated by medication, surgical repair and surgical replacement.

The Carpentier-Edwards PERIMOUNT Magna Ease Pericardial Bioprosthesis Model 3300TFX is a trileaflet valve comprised of bovine pericardium that has been preserved in a buffered glutaraldehyde solution and mounted on a flexible cobalt-chromium alloy frame. It is intended for patients who require replacement of their diseased, damaged or malfunctioning native or prosthetic aortic valve and whose prognosis without aortic valve replacement is unacceptably poor in terms of survival, quality of life, or both in the opinion of the attending physicians.

## **4. STUDY OVERVIEW**

### **4.1 PURPOSE**

The primary objective of the investigation is to obtain long-term human clinical data in order to demonstrate that the Carpentier-Edwards PERIMOUNT Magna Ease is a safe and effective replacement aortic bioprosthesis.

### **4.2 ENDPOINTS**

#### **4.2.1 PRIMARY SAFETY ENDPOINTS**

Long term safety performance will be evaluated by comparing the linearized yearly rates listed below to the objective performance criteria (OPC) referenced in the Food and Drug Administration (FDA) 1994 Draft Heart Valve Guidance [2].

OPC's from the Heart Valve Guidance are:

- Thromboembolism
- All Hemorrhage
- All Perivalvular Leak
- Endocarditis

#### **4.2.2 SECONDARY SAFETY ENDPOINTS**

Descriptive information of early rates, late linearized rates and actuarial analysis of the following:

- Thromboembolism
- Valve thrombosis
- All hemorrhage
- Major hemorrhage
- All perivalvular leak
- Major perivalvular leak
- Endocarditis
- Hemolysis
- Structural valve deterioration

- Non-structural valve dysfunction
- Reoperation
- Explant
- Death
- Valve-related death

Blood Data (white blood count, red blood count, hematocrit, hemoglobin, platelet count, serum lactate dehydrogenase, haptoglobin and reticulocytes).

#### 4.2.3 PRIMARY EFFECTIVENESS ENDPOINTS

The primary effectiveness endpoint will be:

Proportion of subjects in NYHA Functional Classification I and II at 8 years post-implant.

#### 4.2.4 SECONDARY EFFECTIVENESS ENDPOINTS

The secondary effectiveness endpoints will be:

Hemodynamic Performance by echocardiography at 8 years post implant, which includes:

- Peak Gradient
- Mean Gradient
- Effective Orifice Area
- Effective Orifice Area Index
- Performance Index
- Cardiac Output
- Cardiac Index
- Severity of aortic regurgitation

Quality of Life Survey (EQ-5D)

## 5. STUDY DESIGN

This is a prospective, single-arm, multi-center study to be conducted in the US and outside the US (OUS). A minimum of 225 subjects will be implanted (Section 11.1 Sample Size) to obtain long term data from 101 subjects at 8 years post implant of the Carpentier-Edwards PERIMOUNT

Magna Ease Pericardial Aortic Bioprosthesis, Model 3300TFX (Magna Ease valve). Subject enrollment will not start in the US before obtaining FDA approval of this post approval study.

## 5.1. STUDY SITE SELECTION

Up to 20 sites will enroll subjects in this study. Participating sites will be chosen based on their experience in conducting clinical studies, their experience implanting bioprostheses, excellent academic and medical reputation, as well as their ability to obtain a robust patient population. Each of the centers is required to have a study coordinator to assist the primary investigator(s). In addition, each participating center must have the time and resources available to participate in this study.

Study sites will be in the United States, and outside the US (OUS). On average, each site is expected to implant the Magna Ease valve in at least 15 subjects until enrollment requirements are met. It is anticipated that each of the participating sites will have a Principal Investigator, and there will be up to six Co-Investigators per site, for a total of up to 140 investigators. Each of the operating investigators will be experienced in aortic valve replacement surgery.

## 5.2. STUDY TIMELINE

Expected timeline for study implementation:

**Table 1: Expected timeline for study implementation**

Study Milestone	Timeframe in Quarters (3 months)	Cumulative Subject Enrollment
FDA protocol approval	Q0	0
Study Site Start-up • 1-2 IRB approvals / month	Q1 – Q3 (3 months – 9 months)	40 - 86*
First subject enrolled	Q1 – Q2 (3 months – 6 months)	87
Enrollment Phase • 1-3 subjects / quarter / site	Q2	107
	Q3	123
	Q4	143
	Q5	170
	Q6	194
	Q7	218
Completion of Subject Enrollment	Q8	225
Completion of Follow-up	101 subjects complete 8 year assessment	
Final Study Report Submission	Q1 after last subject completes follow-up	

\* Subjects already enrolled outside U.S. (OUS)

## 6. PATIENT POPULATION

Patients undergoing valve replacement of the diseased native aortic valve or previously implanted prosthesis will be considered for this study if they sign the subject informed consent form preoperatively, and meet all inclusion criteria and none of the exclusion criteria.

The routine practice of cardiovascular surgery employed by the principal investigator will determine the indications for replacement of a patient's natural valve or previously implanted prosthesis. Due to the complexity and variations in surgical procedures, and the individual anatomy and other patient related factors, the choice of surgical technique and approach is left to the discretion of the individual surgeon.

### 6.1 ENTRY CRITERIA

Patients will have to preoperatively sign the subject informed consent form, and meet all inclusion criteria and none of the exclusion criteria as indicated below to participate in this clinical study. The investigator will determine and document whether each patient meets the selection criteria before enrollment into the study. Subjects will be considered enrolled for study participation at the time the patient signs the subject informed consent form. A subject identification number will be assigned to each enrolled subject. If an enrolled subject does not receive the study valve an explanation will be indicated on the Case Report Form (CRF). The subject will be discontinued from the study and no further CRFs will be completed for these subjects. If a non-study tissue valve or a mechanical valve is implanted in an otherwise eligible subject, the reason for implanting the non-study valve must be documented in the Subject Screening Log. Reasons for implant of a non-study tissue valve in the aortic position include the subject's refusal to participate, withdrawal from the study, etc. Documentation of these cases is important to prevent bias in subject selection. Subjects censored from the study will be identified and the reason for censorship will be indicated.

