### 6.3 EXCLUSION CRITERIA

1. The patient has any known non-cardiac life-threatening disease, which will limit the patient's life expectancy below 1 year.
2. The patient presents with active endocarditis within the last 3 months.
3. The patient has an abnormal calcium metabolism (e.g., chronic renal failure, hyperparathyroidism).
4. The patient has an aneurismal aortic degenerative condition (e.g., cystic medial necrosis, Marfan's syndrome).
5. The patient is pregnant or lactating.
6. The patient is an intravenous drug abuser.
7. The patient is currently a prison inmate.
8. The patient is currently participating in a study of an investigational drug or device.
9. The patient requires replacement of a native or prosthetic mitral, tricuspid or pulmonic valve.
10. The patient requires a repair of the mitral or tricuspid valve with the use of an annuloplasty device.
11. The patient was previously enrolled in the study.
12. The patient had a prior mitral, tricuspid or pulmonic valve surgery, which included implantation of a bioprosthetic valve, mechanical valve, or annuloplasty ring that will remain *in situ*.

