where  $p$  is the proportion of the subjects in NYHA Class I or Class II at 8 years post implant. The expected proportion of the alive subjects in NYHA class I or II at eight years is above 90%, based on 8 year follow up data for the Carpentier-Edwards PERIMOUNT 2700/2800/2900 valve (this proportion is above 90% within the subjects with valid NYHA assessment at each annual visit till 8 years follow up). Based on this expected proportion, a sample size of 45 subjects provides 85% power to test the hypothesis that the true proportion is greater than 75% using an exact binomial test. Thus, the sample size of 101 subjects with NYHA data at 8 year post implant is more than adequate to provide sufficient power.

The calculated number of subjects ( $n$ ) that must be enrolled in order to have 101 subjects survive to 8 years post implant with 99% probability is based on the binomial distribution. Specifically,  $n$  is such that

$$1 - \sum_{x=1}^{101} \binom{n}{x} p^x (1-p)^{n-x} > 99\%$$

where  $p$  is the probability that a subject will survive for 8 years post implant. This calculation can be performed using standard statistical software. Based on the reported 8-year survival of 60% from Aupart, et al. (2006) [8], a sample size of 195 subjects fulfills the requirements of the equation above. Based on the data collected in a previous post approval study conducted by

---

PROPRIETARY DATA: This document and the information contained herein may not be reproduced, used or disclosed without written permission from Edwards Lifesciences LLC.

Edwards (Study 98-1), a lost to follow-up rate of 7.8% was observed among subjects who reached 5 or more years of follow-up post implant. The sample size is further inflated to 225 to account for up to a 15% rate of lost to follow up.

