## 11.2 ANALYSIS POPULATION

All the data collected up to the point of the explant or expirations will be included in the safety and effectiveness analyses. The primary safety analysis will include all the enrolled subjects. The primary effectiveness analysis will include the subjects who survived post implant and have at least one post-implant NYHA assessment.

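### Enrollment is fixed at consent, yet the primary safety set is all enrolled subjects and the 225 target is counted both as enrolled and as implanted; the early event percentages and actuarial curves need an implanted-subject set.

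*Combined protocol and SAP*

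**What the plan says.** Section 6.1 sets the moment of enrollment: "Subjects will be considered enrolled for study participation at the time the patient signs the subject informed consent form". It foresees that some enrolled subjects will not receive the study valve and says of them: "The subject will be discontinued from the study and no further CRFs will be completed for these subjects".

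The target of 225 appears in two forms.

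- As implanted. Section 1: "This study will enroll a minimum of 225 patients implanted with the study valve". Section 5: "A minimum of 225 subjects will be implanted", with a pointer to Section 11.1.
- As enrolled. Table 1 places 225 in its cumulative enrollment column, in the row "Completion of Subject Enrollment". Section 11.1 derives the number of subjects "that must be enrolled in order to have 101 subjects survive to 8 years post implant with 99% probability".

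Section 11.2 then defines the safety set: "The primary safety analysis will include all the enrolled subjects". Section 11.3.1 summarizes early events as a percentage of subjects with an event in the 30 days after implant, late events as a rate per year of subject survival, and freedom from each event by Kaplan-Meier.

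**The concern.** Under Section 6.1, 'enrolled' and 'implanted' are different counts, and the plan uses them interchangeably in two places where the difference matters.

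The first is the safety set. A subject who consents but gets no study valve has no study-valve implant date and no follow-up forms. Such a subject cannot have an event within 30 days of implant, yet under Section 11.2 would sit in the denominator of that percentage. The resulting error favors the device. The same subject has no starting point on an actuarial curve that runs from implant.

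The second is the accrual count. The only inflation in Section 11.1 is for loss to follow-up, so nothing covers subjects who consent and are not implanted. If accrual were closed at 225 consents, part of the loss-to-follow-up margin behind the 101 eight-year subjects would be used up before follow-up began.

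**Working it through.** **Inputs from Section 11.1.** 101 subjects at 8 years with 99% probability; 8-year survival 60%; 195 subjects before inflation; inflation to 225 for up to 15% loss; 7.8% loss observed in Study 98-1; 800 life-years needed for the safety test.

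**Assumed.** The share f of consented subjects never implanted is not in the documents; 2%, 5%, 10% and 15% are used as a range. Survival and loss to follow-up are taken as independent. Valve counts are rounded down.

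**1. The plan's own figures.** With X binomial(n, 0.60), P(X >= 101) is 0.9896 at n = 194 and 0.9917 at n = 195, so 195 is the smallest n above 99%. (The sum as printed runs to 101, which gives P(X >= 102) and n = 196, a trivial difference.) Then 195 x 1.15 = 224.25, rounded up to 225. Both stated figures reproduce, and neither step includes an allowance for non-implantation. Survival is counted post implant, so n makes sense only as a number of valve recipients.

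**2. If 225 meant consents.** Valves = 225 x (1 - f). The probability of being alive and followed at 8 years is 0.60 x 0.922 = 0.5532 at 7.8% loss, and 0.60 x 0.85 = 0.51 at 15% loss.

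| f (assumed) | Valves | P(at least 101), 7.8% loss | P(at least 101), 15% loss | Consents for 225 valves |
|---|---|---|---|---|
| 0% | 225 | 99.9% | 97.1% | 225 |
| 2% | 220 | 99.8% | 94.3% | 230 |
| 5% | 213 | 99.1% | 86.7% | 237 |
| 10% | 202 | 94.4% | 63.9% | 250 |
| 15% | 191 | 77.4% | 32.8% | 265 |

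At 7.8% loss the smallest number of valves giving more than 99% is 213, so the tolerable share is (225 - 213)/225 = 5.3%. In the 15% column the probability is below 99% even with 225 valves. That shortfall exists before any non-implantation, so only the further fall down the column belongs to this point.

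**3. Early percentages.** If a share f of the denominator cannot have the event, the reported percentage is the true percentage x (1 - f). For an illustrative 2.0%: 2.0 x 0.95 = 1.9% at f = 5%, and 2.0 x 0.90 = 1.8% at f = 10%.

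**4. Primary linearized rates.** The denominator is subject-years. A subject discontinued without further forms adds practically no time and no events, so the comparison with 2 x OPC does not move. Total exposure is also safe. With constant mortality and 60% alive at 8 years, the hazard is -ln(0.6)/8 and mean time to 8 years is 0.4 x 8 / (-ln 0.6) = 6.264 years. Even 191 valves give 191 x 6.264 = about 1,196 subject-years. If 15% of those subjects contributed nothing, 1,196 x 0.85 = about 1,017 would remain, against 800 needed.

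**5. Effectiveness.** Sections 11.2 and 11.4 require survival of the implant and at least one post-implant NYHA assessment, so never-implanted subjects are already outside that set.

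**The case against.** The strongest defense is that the two statements setting the target, in Sections 1 and 5, both make implants a minimum. Section 5 refers to Section 11.1 for the number, which identifies that number as an implant count. Section 5.1 speaks of each site implanting valves until the enrollment requirement is met. Table 1 is an expected timeline and not a stopping rule. Section 14 requires a completed form for each subject who receives a study valve, so valve recipients are the natural safety set. Most of this stands. It shows which reading was probably meant, but leaves Section 11.2 saying something else.

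A reader might infer three stronger conclusions, and the documents support none of them.

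- That accrual will stop short of 225 valves. This follows only if Table 1 and Section 11.1 override Sections 1 and 5. The rule in Section 10.6 against replacing withdrawn subjects does not settle it, because that paragraph concerns patients in follow-up.
- That never-implanted subjects distort the primary safety test. They contribute no exposure, so they do not. The early percentage is a descriptive summary.
- That exclusion 11, "The patient was previously enrolled in the study", shuts out patients who consent and are then found ineligible or have surgery deferred. Section 6.1 has eligibility determined and documented before enrollment, so a patient found ineligible at that step was never enrolled. No limit on the time from consent to surgery is stated, so a deferred patient can stay enrolled.

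**Conclusion.** The inconsistency is real and should be corrected, but its reach is limited. As written, the safety set contains subjects without a valve or an implant date. The early percentages are then understated by the relative amount f, and the actuarial analyses cannot place those subjects. The primary linearized-rate tests, the 800 life-years and the effectiveness analysis are essentially untouched.

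The accrual consequence is conditional. It arises only if 225 is counted as consents. With 60% survival, 7.8% loss and independence, it breaches the 99% target only when more than about 5% of consented subjects go without the valve; the probability is 94.4% at an assumed 10%. The size of both effects rests on f, which the documents do not give.

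**What to change.** In Section 11.2, define the primary safety set as all subjects who receive the study valve, with time counted from implant, and list consented-but-not-implanted subjects separately with the reason. A set based on attempted implantation would not do: it would still admit subjects without a valve, for whom Section 6.1 ends data collection. In Table 1 and Section 11.1, replace 'enrolled' and 'enrollment' by 'implanted' where the 225 is counted, so that the figure matches Sections 1 and 5. Exclusion 11 can stay as it is.

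The cost is a few words in three places. Reported early percentages would be slightly higher than under the literal reading. Reaching the 225 implants already promised would take some extra consents: 237 - 225 = 12 at an assumed 5% not implanted, and 250 - 225 = 25 at 10%.

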### 10.5 EXPLANTED VALVES

Every effort should be made to return the explanted valve(s), at autopsy or explantation to Edwards. The explanted valve should be placed in a container with a suitable histological fixative such as 10% formalin or 2% glutaraldehyde immediately after excision and returned to Edwards. Refrigeration is not necessary under these circumstances. Contact Edwards Clinical Research for additional instructions.

Any pertinent information, e.g. operative notes, autopsy report etc should be sent to Edwards. This information should be redacted at the site to remove any identifying information (i.e. subject full name, personal identification numbers, address, etc.).

After the study valve is explanted, the subject will be followed for either an additional 30 days to monitor for any new adverse events or until all study device related serious adverse events (see section 9.1) are resolved. After that point the subject will be discontinued from the study. No further evaluations and/or case report forms are needed after study exit. Data from these subjects will be included in analysis.

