### **14. CASE REPORT FORMS**

CRFs for individual subjects will be provided by Edwards [REDACTED]. The principal investigator or designee must keep a separate log of subject names and current addresses to facilitate record keeping and his or her ability to contact subjects for future follow-up.

CRFs are used to record study data and are an integral part of the study and subsequent reports. Therefore, the reports must be legible and complete. In order to comply with the HIPAA regulations and European data protection laws, any information related to the subject's identity must be redacted. All forms should be filled out using a ballpoint pen. Errors should be corrected by drawing a single strikethrough in ink, initialed and dated by the person who makes the change on the day the change is made. Copies of the changed form must be provided to the sponsor and retained in the subject study file.

A CRF must be completed and signed by the principal investigator, co-investigator or his or her designee listed in the Delegation of Authority form for each subject receiving a study valve, including subjects withdrawn from the study for any reason. The reason for withdrawal must be noted on the CRF, by the investigator.

Since there is a potential for errors, inaccuracies, and illegibility in transcribing data onto CRFs, originals or photocopies of all relevant operative records and reports, postoperative examinations, laboratory and other test results must be kept on file. CRFs and copies of test results must be available at all times for inspection by the study sponsor, the study monitor, and authorized regulatory bodies.

CRF's must be kept current to reflect subject status at each phase during the course of the study. Instructions for CRF collection or submission are provided in the CRF synopsis.

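### Section 6.1 does not separate a study valve that was tried and removed in the same operation from one never offered, so attempted implants may be left out of the early (30-day) safety rates

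*Combined protocol and SAP*

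**What the plan says.** Four parts of the combined protocol and SAP bear on this.

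- **Section 6.1** fixes enrolment at consent: "Subjects will be considered enrolled for study participation at the time the patient signs the subject informed consent form". An enrolled subject who does not get the study valve has the reason entered on the CRF, and then: "The subject will be discontinued from the study and no further CRFs will be completed for these subjects". Where another valve is implanted in an otherwise eligible subject, "the reason for implanting the non-study valve must be documented in the Subject Screening Log". The examples given there for a non-study tissue valve are refusal and withdrawal, in an open-ended list. A valve tried and abandoned is not named.
- **Section 11.2** says: "The primary safety analysis will include all the enrolled subjects".
- **Section 14** requires a completed, signed CRF "for each subject receiving a study valve, including subjects withdrawn from the study for any reason".
- **Section 10.5** says that after an explant "the subject will be followed for either an additional 30 days to monitor for any new adverse events", or until device-related serious events resolve, and that these subjects' data are analysed.

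Section 11.3.1 counts early events within 30 days of implant. None of the endpoints in Section 4.2 counts a failed or abandoned implantation.

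**The concern.** Consider a subject in whom the study valve is placed in the annulus, found unsatisfactory, and exchanged for another manufacturer's valve before the operation ends. That subject leaves surgery without a study valve. On the ordinary meaning of the word, the subject did not receive one, so the Section 6.1 exit rule applies and postoperative forms stop. Had the same valve come out a day later, Section 10.5 would clearly have applied.

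What is at stake is the early safety picture: 30-day event percentages, early death, and the first part of the freedom-from-event curves. Dropping such subjects can only remove early events from the counts. It lowers the early percentages if their early risk exceeds that of successfully implanted subjects. The point is relevant to this device because Section 7.1 gives easier implantation in small aortic roots as the reason for the reduced profile. Section 6.1 itself gives prevention of selection bias as the reason for documenting non-study-valve cases.

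**Working it through.** **1. The passages side by side, for a subject whose study valve was placed and removed in the same operation**

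| Provision | Does it capture this subject? |
|---|---|
| 6.1, exit rule | On the natural reading, one explanation and then no further forms |
| 11.2, safety population | In the population, since enrolment is at consent, but without postoperative data if 6.1 applies |
| 8.2 and Table 3, operative form | Intra-operative events, if the form is completed; 6.1 and 14 leave this unclear |
| 10.2, 24-hour reporting | Device-related events during the study; the subject has been discontinued |
| 10.4, deaths | Deaths while participating, or within 30 days of an explant |
| 10.5, explants | Yes, if the site classes the removal as an explant; nothing says whether it should |
| 11.3.1, early rates | The clock starts at implant, which is undefined for this subject |

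Capture therefore depends on how each of up to 20 sites (Section 5.1) reads 'receive' and 'explant'. Even under the explant reading, 11.2 speaks of data up to the point of explant while 10.5 includes data from explanted subjects followed for 30 days. The two need to agree.

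**2. The plan's own figure**

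Section 11.1 needs n such that at least 101 survive 8 years with 99% probability at 60% survival. With n = 195, P(X ≥ 101) = 0.9917, which reproduces 195. Then 195 × 1.15 = 224.25, which gives 225. Section 5 counts implanted subjects, so this point does not affect the sample size.

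**3. How many subjects**

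The documents give no abandonment rate. Assumed range 0.5% to 2%: 0.005 × 225 = 1.1 and 0.02 × 225 = 4.5, so about 1 to 5 subjects.

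**4. Effect on an early percentage**

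Let f be the share of attempts abandoned, e the early event risk in implanted subjects, and q the risk in abandoned attempts. All three are assumed.

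Risk among all attempted = (1 − f)·e + f·q

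Example: f = 2%, e = 2%, q = 50% gives 0.98 × 2% + 0.02 × 50% = 1.96% + 1.00% = 2.96%.

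With q from 10% to 50%:

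| f | Reported 2% becomes | Reported 3% becomes |
|---|---|---|
| 0.5% | 2.0–2.2% | 3.0–3.2% |
| 1% | 2.1–2.5% | 3.1–3.5% |
| 2% | 2.2–3.0% | 3.1–3.9% |
| 5% (stress case) | 2.4–4.4% | 3.4–5.4% |

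If abandoned attempts enter the denominator under 11.2 but contribute no events, the reported figure is diluted instead: at f = 2%, 0.98 × 2% = 1.96%.

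**5. Effect on the primary rates**

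Section 11.3.1 reports linearized rates for events after 30 days, so 30-day data on these subjects would add nothing to them. If early events were counted in the primary test, each extra event would add at most 1/808 = 0.12 per 100 subject-years, against limits of 2 × 1.2 = 2.4 to 2 × 2.5 = 5.0.

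**The case against.** The strongest reply is that the documents never mention an abandoned attempt. A valve seated and then removed can be read as explanted, and 10.5 sets no minimum time in place. Several provisions would also record part of the case: the CRF explanation, the screening log, intra-operative events, device-event reporting and death reporting. The affected rates are descriptive secondary outcomes in a study whose purpose is long-term data. Following a subject who carries another valve also mixes in events due to that valve.

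Much of this stands, and it rules out four stronger readings that a reader might infer:

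- *That these subjects appear in no endpoint.* The documents do not go that far: 11.2 nominally includes them, and the provisions above may catch part of their data.
- *That Section 14 requires forms only for recipients.* It requires them for each recipient and does not say 'only'; 6.1 itself asks for a CRF entry for non-recipients.
- *That abandoned attempts are device failures.* No causes are given. Section 8.2 stresses sizing and orientation, and leaves technique to the surgeon. A subject switched to another of the six sizes of the same model has still received a study valve.
- *That early device removals are understated by a third to over two thirds.* That is 1/(1 + 2) to 5/(5 + 2): a ratio of assumed counts, with two other early explants also assumed, and it treats an intra-operative exchange as an explant.

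What the reply does not remove is the ambiguity. The provisions cited either stop at the end of surgery, apply only during participation, or depend on calling the removal an explant.

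**Conclusion.** The point holds as a minor one. Section 6.1 applies a single exit rule to two different kinds of subject, and that rule does not fit with 11.2 or 10.5. Attempted implants may therefore be missing from the early safety rates, and where they carry higher early risk the omission favours the valve.

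The likely size is small: about 1 to 5 subjects, and under the assumed 0.5–2% range a shift of at most about 1 percentage point in an early percentage (2% to 3.0%), usually less. Larger shifts need abandonment to be frequent as well as harmful. The conclusion about the rule rests on the ordinary meaning of 'receive'. The size rests entirely on assumed rates. The sample size is untouched and the primary linearized rates change little.

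**What to change.** - **6.1:** define an attempted implant as a study valve placed in the annulus where the subject leaves surgery without a study valve. State that the exit rule applies only to subjects with no attempt, who leave as now.
- **6.1, 11.2 and 14:** reconcile the passages so that attempted-implant subjects stay in the safety set, have the operative form completed, and have adverse events and death collected for 30 days, as 10.5 already does after explant. State the day from which the early window runs for them.
- **Reporting:** show these subjects on a separate line, attempted but not implanted, beside the early explant rate. Folding them into early explants would redefine that endpoint.

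Cost: a short amendment, existing forms, and a few extra 30-day follow-ups. Some recorded events will be attributable to the replacement valve, which the separate line makes visible, and the early safety figures may look slightly less favourable.
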